**REVISION HISTORY**

Revision #	Version Date	Summary of Changes	Consent Change?
1	1/29/20	Adding 2 MRI scans	yes
2	3/30/23	1) Adding 15 patients. 2) All new patients will receive medium-dose lithium therapy. 3) The Week-12 study visit will be eliminated. 4) There will be some changes to the blood-based biomarkers assessed.	yes
3	5/30/23	Added language required by CTSC regarding MRI data storage and transmission.	no
4	11/30/23	Parking fee reimbursement for subjects	no

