### 1.0 Study Summary

Study Title	Repurposing lithium as a disease-modifying therapy in Parkinson's disease: A Phase I trial
Study Design	Open-label
Primary Objective	Determine if medium-dose lithium aspartate therapy in an additional 15 patients is associated with similar improvements in blood-based therapeutic targets and MRI-based biomarkers as observed in the previous four patients receiving this dosage.
Secondary Objective(s)	Determine the tolerability of medium-dose lithium aspartate when titrated to a dosage of 30-45mg/day.
Research Intervention(s)/ Investigational Agent(s)	Lithium aspartate.
IND/IDE #	IND exempt (#135530)
Study Population	Parkinson's disease (PD)
Sample Size	15
Study Duration for individual participants	25-27 weeks
Study Specific Abbreviations/ Definitions	Parkinson's disease (PD), Over-the-counter (OTC)

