**Table 1: Mean FW Longitudinal Changes from Pilot Lithium/PD Trial, UF and PPMI Longitudinal Cohorts**

	Mean Change in DMN-T FW	Mean Change in nbM FW	Mean Change in pSN FW
High-Dose Lithium (24-Week Changes)	-0.0117 (n=2)	-0.0140 (n=2)	0.0198 (n=2)
Medium-Dose Lithium (24-Week Changes)	-0.0098 (n=2)	-0.0416 (n=2)	-0.0307 (n=2)
Low-Dose Lithium (24-Week Changes)	0.0123 (n=2)	-0.0306 (n=2)	0.0787 (n=2)
PD from UF (1-Year Changes)	---	---	0.038  (n=25)
Aged-Matched HCs from UF (1-Year Changes)	---	---	0.001  (n=19)

PD from PPMI (1-Year Changes)	0.0100 ± 0.030  (n=130)	0.0025 ± 0.041  (n=130)	0.0180 ± 0.055  (n=103)
Aged-Matched HCs from PPMI (1-Year Changes)	0.0005 ± 0.024  (n=58)	-0.0085 ± 0.034  (n=58)	0.0070 ± 0.030  (n=49)

FW: free water, PD: Parkinson's disease, UF: University of Florida, PPMI: Parkinson's Progression Markers Initiative, DMN-T: dorsomedial nucleus of the thalamus, nbM: nucleus basalis of Meynert, pSN: posterior substantia nigra, HC: healthy control.

In summary, this pilot study showed medium-dose lithium therapy to have the most robust therapeutic target engagement of PBMC Nurr1 and SOD-1 mRNA expression and the most robust improvements in known MRI disease-progression biomarkers but to also have a high rate of side effects. Also, these results stem from only four and two patients receiving this lithium dosage with blood-based and MRI biomarker data, respectively. If similar results were found in a larger number of PD patients treated with medium-dose lithium therapy in a manner to improve clinical tolerability, such preliminary data would form a strong grant application to the Michael J Fox Foundation and/or the NIH to support a larger RCT.

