## 5.0 Study Design\*

*5.1 Describe and explain the study design (e.g. case-control, cross-sectional, ethnographic, experimental, interventional, longitudinal, observational).*

Response:

We will enroll 15 additional PD patients within five months. Eligible patients will have PD for <4 years diagnosed by a movement disorder specialist (Drs. [name] or [name]), be 45-80 years old, have normal thyroid and renal function at the screening visit, have no previous exposure to lithium therapy, have no history of brain surgery, have no hx of brain imaging findings suggesting another neurological condition besides PD, have no use of tobacco or THC products for >1 year, have stable PD medications for >30 days without current need for adjustments in the investigator's opinion, and have stable psychiatric and diuretic medications for >60 days with no anticipated need for changes for at least 24 weeks.

All patients will receive medium-dose lithium aspartate therapy (30-45mg/day) for 24 weeks ensuring that the study will be completed within 12 months. The following dose titration will be used in order to minimize side effects: 10mg bid x 1 week, then 15mg bid x 1 week, then 20mg bid x 2 weeks, then 20mg qAM and 25mg qhs thereafter. Patients will be contacted weekly over the first 4-6 weeks to assess for side effects that are likely to be due to lithium, such as sedation, dizziness or confusion. If side effects occur and are bothersome to the patient, the dose will be decreased incrementally to a minimum of 30mg/day. Such a design will enable identification of the maximum tolerated dose for study in a future trial and maximize the number of patients receiving the most promising dose (45mg/day) identified in the previous pilot clinical trial. Blood-based biomarkers and MRIs will be assessed at baseline and 24 weeks.

The primary blood-based biomarker outcome measure will be change in PBMC Nurr1 mRNA expression from baseline to 24 weeks, which will be compared with the data from the three control PD patients from the pilot study using ANCOVA. PBMC mRNA expression will be assessed by quantitative real-time PCR using TaqMan probes to match the pilot study's methodology. Based on the

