## 7.0 Local Number of Subjects

7.1 *Indicate the total number of subjects that will be enrolled or records that will be reviewed locally.*

Response: 15 additional patients (total of 34 including the 19 who have completed the study).

7.2 *If applicable, indicate how many subjects you expect to screen to reach your target sample (i.e. your screen failure rate).*

Response: 20

7.3 *Justify the feasibility of recruiting the proposed number of eligible subjects within the anticipated recruitment period. For example, how many potential subjects do you have access to? What percentage of those potential subjects do you need to recruit?*

Response:

Recruitment will occur from the PI's and [name] movement disorder clinic patients. The PI and [name] care for approximately 500 PD patients of which approximately 70% will be eligible. PD patients are anticipated to be highly interested in participating in this study since there currently are no disease-modifying therapies available for PD. Indeed, 18 PD patients have already voiced

interest in joining the study after being briefly informed of the study's rationale and procedures.

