**Statistical analyses:**

All statistical analyses of outcomes at each time point will be performed using identical methodologies. The statistical assessment of each considered outcome will be based on a standard analysis of variance (ANOVA) model. In this case, each outcome will be fit as a function of randomized group assignment, baseline cognition, and the interaction between group assignment and baseline cognition. Rather than utilizing the null distribution associated with the classic tests for treatment differences within the ANOVA framework which is dependent on the validity of distributional assumptions, an exact permutation testing approach will be utilized. The randomization mechanism at work is a crucial component in this study in that it will be used to create the randomization distribution by which statistical significance will be determined. Reported p-values will be obtained from the permutation distributions of the test statistics based on 10,000 Monte Carlo simulations. All possible pairwise comparisons will be made between the three treatment groups in conjunction with a Bonferroni adjustment for multiple comparisons performed at a 0.05 family-wise error rate. All statistical tests will be two-sided. In addition, since the comparability of treatment groups may be questioned due to chance imbalance in confounding variables, covariates will be added to the above models as a series of secondary analyses. The interaction of patient covariates and randomized assignment will be examined so to assist in the identification of patient subgroups of interest. All adverse events will be recorded during the study period and then tabulated at the end of the study along with the results of the physical exams. All available data from subjects who fail to complete this study will be included in the safety summaries. The probability of an adverse event will be estimated for each treatment group along with the 95% exact confidence interval based on the method of Clopper and Pearson. All analyses will be carried out using SAS version 9.4 (or higher) statistical software (Cary, NC).

*19.2 If applicable, provide a power analysis.*

*NOTE: This may not apply to certain types of studies, including chart/records reviews, survey studies, or observational studies. This question is asked to elicit*

*whether the investigator has an adequate sample size to achieve the study objectives and justify a conclusion.*

Response: N/A

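### Section 19.1 still specifies the pilot's randomised three-group inference, which cannot be estimated in the current single arm of 15 and contradicts Section 5.1; neither section tests the primary objective

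*Combined protocol and SAP*

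**What the plan says.** **Section 19.1, Statistical analyses.** Every outcome is to be analysed with one ANOVA model: "each outcome will be fit as a function of randomized group assignment, baseline cognition, and the interaction between group assignment and baseline cognition". P-values come from a permutation distribution that the text derives from the study's randomisation, with 10,000 Monte Carlo draws. Then "All possible pairwise comparisons will be made between the three treatment groups in conjunction with a Bonferroni adjustment for multiple comparisons", at a family-wise level of 0.05. The paragraph ends with adverse-event tabulation and Clopper-Pearson intervals.

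**Section 5.1, Study Design.** "All patients will receive medium-dose lithium aspartate therapy (30-45mg/day) for 24 weeks". No randomisation of these patients is described there or in Section 12.1. For the primary blood outcome, the 24-week change in PBMC Nurr1 mRNA, the plan is a comparison "which will be compared with the data from the three control PD patients from the pilot study using ANCOVA". Free water in the three brain regions is to be compared by ANCOVA with natural history from the UF and PPMI cohorts.

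**Sections 1.0 and 2.1, primary objective.** The question is whether medium-dose therapy in 15 more patients "is associated with similar improvements in blood-based therapeutic targets and MRI-based biomarkers as observed in the previous four patients receiving this dosage". Section 4.1, below Table 1, says that "these results stem from only four and two patients receiving this lithium dosage with blood-based and MRI biomarker data, respectively".

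**The concern.** Section 19.1 is the protocol's designated analysis plan and claims to cover each outcome, yet its inferential text fits a different trial. The completed pilot randomised 16 patients to three lithium doses (Section 4.1). The Revision History records for Revision 2 that "All new patients will receive medium-dose lithium therapy", and the current Sections 1.0, 5.1 and 12.1 agree with that. The current Section 19.1 does not.

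Three things are at stake:

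- The between-group test written in 19.1 does not exist for the new patients.
- If its permutation method were carried over to a comparison of new patients with historical controls, the p-value would be presented as resting on a randomisation that never took place.
- A difference from untreated controls, even a clear one, would not show that the new results resemble those of the earlier medium-dose patients, which is what the objective asks.

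**Working it through.** **Inputs**

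- Arms now: 1. New patients: 15 (Sections 1.0, 5.1, 7.1, 12.1).
- Pilot: 16 patients randomised to three dose groups, plus 3 untreated controls described as additional to the 16 (Section 4.1). 16 + 3 = 19, and 19 + 15 = 34, the total in Section 7.1.
- Section 19.1 model: group, baseline cognition and their interaction; family-wise level 0.05.
- Section 5.1 sample-size statement: SD 22%, effect 540%, 95% power, two-sided alpha 0.05, two patients needed.

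**Step 1. The plan's own figure.** The effect is 679 − 139 = 540 percentage points (medium dose minus control). With n per group = 2[SD(z₀.₉₇₅ + z₀.₉₅)/Δ]²:

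2 × [22 × (1.960 + 1.645)/540]² = 0.043, rounded up to 1 per group, or 2 in total.

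This reproduces the stated two patients. A noncentral-t check with 2 treated and 3 controls gives power of about 1.00. The statement covers Nurr1 only and takes its SD from three controls. What matters here is that it is a two-group calculation with no Bonferroni correction. It belongs to Section 5.1's contrast, not to Section 19.1's.

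**Step 2. Pairwise contrasts.** With k groups there are k(k − 1)/2.

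- k = 3: 3 contrasts, Bonferroni level 0.05/3 = 0.0167 each.
- k = 1: 0 contrasts, so the correction has nothing to apply to.

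**Step 3. Estimability.** The model has four columns: intercept, group g, cognition c and g × c. If every patient has g = 1, the group column equals the intercept and g × c equals c. The rank is 2 of 4, so the group and interaction effects are not estimable.

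**Step 4. Permutation distribution.** With 15 patients under one label there is 1 arrangement, so every permutation p-value is 1. Adding the three pilot controls would create one contrast. However, membership of the two groups would be set by study phase, not by chance, so the relabelling would have no randomisation behind it.

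**Step 5. The comparators side by side.**

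| Place | Comparator | Method |
|---|---|---|
| 19.1 | three randomised treatment groups | ANOVA with cognition interaction, permutation p-values, Bonferroni |
| 5.1, Nurr1 | three pilot controls | ANCOVA, covariates not listed |
| 5.1, free water | UF and PPMI cohorts | ANCOVA, covariates not listed |
| 1.0 and 2.1, objective | previous four medium-dose patients | none stated |

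Section 19.1 mentions neither the pilot controls nor the external cohorts. No sentence says which section takes precedence. No row supplies a test or estimate for the last line.

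**Step 6. What still works.** The descriptive summaries, the missing-data text and the Clopper-Pearson interval need only one group. For illustration, 0 of 15 patients with an event gives 0% to 21.8%, and 5 of 15 gives 11.8% to 61.6%.

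**The case against.** **Section 7.1 counts all 34 patients, so 19.1 may be meant for the whole programme.** The wording does fit the 16 randomised pilot patients, which probably explains why it remains. But 19.1 states no pooled analysis. Run on the pilot alone, it leaves out the 15 new patients. Pooled, the medium-dose group with blood data would be at most 4 + 15 = 19, of whom 15 were never randomised, so the basis for a randomisation test is lost.

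**Section 5.1 already gives usable analyses.** This largely stands. For this cohort it names the primary blood and MRI outcomes, the comparators and the method, with alpha and power for Nurr1. A reader might infer that three rival analyses are open to choice after the data are seen. The documents do not go that far: the 19.1 test has no groups to act on in the new arm, and the objective names no method. What remains is one contradiction, between 19.1 and 5.1, and one question without an analysis.

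**Much of 19.1 can be run.** This also stands. Clinical adverse events head the list of primary outcomes in Section 3.0, and their interval estimate works with one group. A reader might infer that the whole section is unusable; only its between-group inference is.

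**The cognition interaction.** A reader might infer that this term would make the group effect very imprecise, or would define it at a cognition score outside the eligible range. That depends on how the covariate is coded. Section 19.1 gives no coding and does not name the cognition scale, and a contrast evaluated at the mean score would not have the problem. The case for deleting the term is that it belongs to a design no longer in use.

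**The objective may be read with the hypothesis.** Section 2.2 speaks of engaging targets, which the Section 5.1 contrasts do address, and Section 4.1 discloses the small pilot numbers. Neither turns the similarity question of Sections 1.0 and 2.1 into an analysis.

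**It is proof-of-concept work.** True, but Section 4.1 intends the results to support a grant application for a larger RCT, and the correction costs almost nothing.

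**Conclusion.** Wrong as written, and to be corrected before outcome data are analysed. In a single arm of 15, the between-group inference in Section 19.1 has 0 contrasts where the text implies 3, a design of rank 2 with 4 columns, and one label arrangement. It contradicts Section 5.1 on comparator and method for the primary biomarkers. The primary objective is matched by no analysis in either section, and its reference group is four patients for blood and two for MRI.

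These conclusions follow from the structure of the design. They rest on one reading: that the 15 new patients all receive the same regimen without randomisation, as Sections 1.0, 5.1 and 12.1 state. The finding does not extend to the descriptive, missing-data or adverse-event interval text.

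**What to change.** Replace the inferential text of Section 19.1 so that it agrees with Section 5.1.

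1. **Blood biomarkers.** One contrast per marker: the new cohort against the three pilot controls, with the baseline value of the same marker as covariate, labelled a non-randomised historical comparison. Section 5.1 names this comparator for Nurr1 only, and Revision 2 changed the panel. For any marker not assayed in the pilot controls, give the within-cohort change with its interval.
2. **MRI.** The 24-week change in each region against a named natural-history comparator on the same time scale, since Table 1 gives cohort changes over 1 year. Adjust for baseline where individual data are available. For posterior substantia nigra, Table 1 lists both UF (0.038) and PPMI (0.0180), so say which is primary. For the other two regions it gives only PPMI.
3. **Deletions.** Remove the wording on randomised assignment, the randomisation distribution, the three-group Bonferroni comparisons and the cognition interaction. Keep the descriptive, missing-data and Clopper-Pearson text, in the singular.
4. **Objective (Sections 1.0 and 2.1).** Restate it as estimating the 24-week change with a 95% CI and comparing it with untreated controls or natural history. Show the pilot medium-dose results (n = 4 blood, n = 2 MRI) beside it descriptively, with no claim of similarity.

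The cost is protocol wording: no added patients, visits or assays. The conclusions become those of a non-randomised comparison, which is what the design supports.

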## **20.0 Confidentiality\***

### **A. Confidentiality of Study Data**

*Describe the local procedures for maintenance of confidentiality of **study data** and any records that will be reviewed for data collection.*

*20.1 A. Where and how will all data and records be stored? Include information about: password protection, encryption, physical controls, authorization of access, and separation of identifiers and data, as applicable. Include physical (e.g. paper) **and** electronic files.*

Response: A study binder will be assembled for each subject that will contain all of the non-biomarker data collected. However, the forms linking subjects' personal identifiable information to their study ID numbers will be kept in a separate folder. This folder and all study binders will be stored in a locked room in a locked cabinet at the study site. These data as well as biomarker data will be entered into an excel file on the coordinator's password protected computer located in this same locked room. The excel file will only contain subject ID numbers and no personal identifiable information.

*20.2 A. How long will the data be stored?*

Response: Indefinitely.

*20.3 A. Who will have access to the data?*

Response: The study coordinator and PI.

*20.4 A. Who is responsible for receipt or transmission of the data?*

Response: The study PI.

*20.5 A. How will the data be transported?*

Response: Electronically.

## **B. Confidentiality of Study Specimens**

*Describe the local procedures for maintenance of confidentiality of **study specimens**.*

- ☐ **N/A:** No specimens will be collected or analyzed in this research.  
(Skip to Section 19.0)

*20.6 B. Where and how will all specimens be stored? Include information about: physical controls, authorization of access, and labeling of specimens, as applicable.*

Response: Subjects' blood samples will be labeled with their ID#, DOB, date and time of collection. Some samples will be stored in a locked freezer at the study site until the time of analysis. Some samples will be immediately transported to the laboratory of [name], 5th floor CTRC. MRI scans will be labeled with subject ID#, DOB, date and time of collection.

*20.7 B. How long will the specimens be stored?*

Response: Indefinitely

*20.8 B. Who will have access to the specimens?*

Response: The study coordinator and PI, [name], and the technician at UB's Chemistry Instrument Center ([name]).

*20.9 B. Who is responsible for receipt or transmission of the specimens?*

Response: The PI.

*20.10 B. How will the specimens be transported?*

Response: By local courier to [name]'s laboratory and UB's Instrument Center.

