22% standard deviation among the three control patients and the 540% treatment effect size for the primary outcome from the pilot study results, only two patients would be needed to detect a difference with 95% power at a 2-tailed alpha of 0.05. Secondary outcome measures will include 24-week changes in PBMC SOD-1 expression, PBMC pS9/total glycogen synthase kinase-3B (GSK-3B) and pThr308, pS473 and t-Akt and plasma interleukin-6 (IL-6) levels. Blood-based biomarkers will be assessed by [name]. Statistical analyses will be performed by [name].

The primary MRI outcomes will be 24-week MRI changes in DMN-T, nbM and pSN FW. Using ANCOVA, these outcomes will be compared with the known natural history of such changes in PD derived from the UF and PPMI longitudinal cohorts summarized in Table 1. In addition, secondary comparisons will be made between changes in these lithium-treated patients and age-matched and disease-duration-matched PD subsets from PPMI.

Exploratory clinical outcomes will include changes in Movement Disorder Society-Unified Parkinson's Disease Rating Scale (MDS-UPDRS) Part III (Motor Examination) with subjects in the "on" state, Montreal Cognitive Assessment (MoCA), Parkinson's Anxiety Scale, Geriatric Depression Scale-15, Fatigue Severity Scale, Insomnia Severity Index and Parkinson's Disease Questionnaire-8. Adverse events and medication compliance will be assessed at a three month phone call. Trough serum lithium and safety labs including HgA1C will be assessed at each visit. Because both baseline and on-treatment lithium levels will mostly be below the level of detection using conventional clinical laboratory services (i.e. Kaleida or Quest), these assays will be performed by the UB Chemistry Instrument Center under the direction of [name]. A protocol was developed by Drs. [name] and [name] for these assays for the pilot study that provided reliable results able to detect baseline lithium levels in all patients prior to initiation of lithium therapy.

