The MRI protocol will include a 3D T1-weighted image that will be optimized with the new Philips 3T scanner. Similarly, a multi-shell diffusion weighted imaging acquisition will also be optimized for free water imaging. We will use a sequence with a longer repetition time (6400ms) in order to avoid aliasing T1 effects. In addition, a b=0 image will be acquired with opposite phase encoding to facilitate susceptibility-induced geometric distortions. 3D T1-weighted images will be corrected for intensity inhomogeneity using the N4 tool and subsequently segmented using the SIENAX tool to obtain partial volume estimate maps of the grey matter. The nbM will then segmented as previously described. Briefly, a histologically defined map of the nbM will be brought into the native 3D T1-weighted image space for each scan via non-linearly warping with Advanced Normalization Tools. In addition, each 3D T1-weighted image will be processed using the FreeSurfer 6.0 pipeline along with the thalamic nuclei segmentation submodule. Outputs will be visually inspected for errors and misclassification. Manual corrections to the FreeSurfer output (e.g., introduction of white matter control points, editing of brain mask, white matter mask) will be made as appropriate. For obtaining a mask of the DMN-T, the following individual nuclei will be combined into a single segmentation: paratenial, reuniens (medial ventral), mediodorsal medial magnocellular and mediodorsal lateral parvocellular. pSN regions of interest (ROI) will be obtained using previously published methodology. Briefly, the b=0 image will be aligned to MNI space using an affine registration. Next, the pSN will be drawn using ROIs that include 10 voxels that span two axial slices on each image. The dorsal slice will contain a rectangular

region of interest of six voxels ( $2 \times 3$ ) and the ventral region of interest will consist of a square region of interest of four voxels ( $2 \times 2$ ). The resulting ROIs will then be brought back into native space using the corresponding inverse transformation. Finally, the nBM and DMN-T maps will be brought into the diffusion space using boundary based registration between the 3D T1-weighted image and the  $b=0$ . The maps of the nBM, DMN-T, and pSN in diffusion space will be used to obtain free water values within each ROI.

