The diffusion-weighted imaging acquisition will be corrected for susceptibility-induced and eddy current/subject movement-induced distortions using a combination of the FSL tools topup and eddy. Next, the corrected diffusion weighted data will be processed with the free water elimination model implemented in DIPY (<https://dipy.org>) to obtain free water maps. Occipital FW changes will serve as an internal quality control since this ROI is known to have relatively small longitudinal FW changes over 1 year in PD. For example, data from PPMI showed 1-year pSN and occipital FW changes in PD to be 11.6% and 0.25%, respectively. In the lithium/PD pilot study, 24-week occipital FW changes ranged from -8% to 5% among the six patients with valid MRI scans. In the proposed study, patients with occipital FW changes of at least 14% from baseline to Week 24 will be excluded from the MRI outcome analyses as such changes would indicate an MRI acquisition anomaly at either visit.

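### No masking of the imaging reader to visit order is planned, and the 14% occipital filter would pass a shared scanner shift larger than a year of pSN change

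*Combined protocol and SAP*

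**What the plan says.** Section 5.1 states that "The primary MRI outcomes will be 24-week MRI changes in DMN-T, nbM and pSN FW", and Section 3.0 also lists them as primary. The three regions are obtained differently (Section 5.1):

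- **pSN:** the b=0 image is aligned to a template, "the pSN will be drawn using ROIs that include 10 voxels that span two axial slices on each image", and the regions are then mapped back to native space.
- **DMN-T:** taken from the FreeSurfer thalamic segmentation. "Outputs will be visually inspected for errors and misclassification", and the plan permits "Manual corrections to the FreeSurfer output".
- **nbM:** an atlas map warped to each scan.

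On labelling, Section 20.6 B says that "MRI scans will be labeled with subject ID#, DOB, date and time of collection". Section 12.2 limits what is entered on the scanner to subject codes. Section 19.1 gives the processing to the imaging centre. Neither of these sections mentions masking to visit, reading order or repeat reading, and Section 19.3, on quality control of data, is answered as not applicable.

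On scan quality, Section 5.1 uses occipital free water (FW) as an internal control because it should hardly move: "data from PPMI showed 1-year pSN and occipital FW changes in PD to be 11.6% and 0.25%, respectively". In the pilot, "24-week occipital FW changes ranged from -8% to 5% among the six patients with valid MRI scans". The rule for this study is that "patients with occipital FW changes of at least 14% from baseline to Week 24 will be excluded from the MRI outcome analyses". The MRI outcomes are compared with the UF and PPMI cohorts; there is no concurrent untreated group.

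**The concern.** There are two separate routes to bias.

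**Reader.** With no untreated arm, a reader who can tell baseline from Week 24 knows which direction of change the study hopes to see. The pSN mean rests on only 10 voxels placed on each image, and the DMN-T segmentation can be edited. A consistent difference in placement or editing between visits goes straight into the change score.

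**Scanner.** The occipital region is measured in every patient but used only as an in-or-out filter. If the cut-off is wider than the change under study, a shift that affects most patients in the same direction is kept. Comparators scanned elsewhere do not share it, so it would not cancel.

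At stake is whether a fall in FW, which the plan wants to use to support a grant application for a larger trial, can be told apart from reader expectation or scanner drift.

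**Working it through.** **Inputs.** From Section 5.1: one-year PPMI change of 11.6% (pSN) and 0.25% (occipital); pilot occipital range of -8% to 5% in six patients; cut-off 14%; 15 patients. From Table 1 (Section 4.1): PPMI one-year pSN change 0.0180, SD 0.055, n = 103.

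**1. The plan's own figures.** The region size reproduces: 2 × 3 + 2 × 2 = 10 voxels. The 11.6% cannot be reproduced, because no baseline pSN FW is given.

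**2. The cut-off against the plan's yardsticks.**
- Against one year of pSN change: 14 / 11.6 = 1.21.
- Against 24 weeks, assuming linear change: 11.6% × 24/52 = 5.35%, and 14 / 5.35 = 2.6.
- Against one year of occipital change: 14 / 0.25 = 56.
- Against the largest pilot value: 14 / 8 = 1.75. That 8% fall is itself 8 / 5.35 = 1.5 times the 24-week pSN change.

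**3. In FW units.** If the 11.6% and the 0.0180 describe the same PPMI data (assumption), baseline pSN FW is 0.0180 / 0.116 = 0.155. A 14% proportional shift is then 0.14 × 0.155 = 0.0217, against 0.0180 in a year and 0.0180 × 24/52 = 0.0083 in 24 weeks. For the other regions a 14% shift exceeds one year of PPMI change if baseline FW is above 0.0100 / 0.14 = 0.071 (DMN-T) or 0.0025 / 0.14 = 0.018 (nbM). Those baselines are not given.

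**4. A shift shared by all 15 patients.** Suppose lithium does nothing, the PPMI comparison is on the same time scale, and every patient has the same downward shift. A two-sample t test (15 against 103, 116 degrees of freedom, two-sided 0.05) stands in for the planned ANCOVA. The standard error is SD × √(1/15 + 1/103) = SD × 0.276.

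| Shared fall | SD 0.055 (Table 1) | SD 0.037 (0.055 × √(24/52), assuming variance grows with time) |
|---|---|---|
| none | 2.5% | 2.5% |
| 8% (0.0124) | 13% | 22% |
| just under 14% (0.0217) | 29% | 55% |

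The entries are the chance of a significant result in the direction of benefit.

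**5. Random shifts.** If shifts vary independently and uniformly within ±14%, their SD is 0.0217 / √3 = 0.0125. The total SD is √(0.055² + 0.0125²) = 0.0564, a rise of 2.6%. The mean is not biased.

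**6. Reader route.** No arithmetic applies. Set side by side, Sections 5.1, 12.2, 19.1, 19.3 and 20.6 B describe placement, editing, labelling and processing, and none keeps visit order from the reader.

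**The case against.** - **The label is an answer to a confidentiality question.** Section 20.6 B concerns storage and labelling, not what the reader sees while placing regions. This stands: the date label alone does not unblind anyone. The gap is that no masking is stated; the label only makes visit order easy to see.
- **A reader might infer that the pSN is hand-drawn freely.** The plan says drawn, in blocks of fixed shape in template space, following a published method not available here. Manual placement is a fair inference, since an atlas or segmentation method is named for the other two regions and none for the pSN, but the degree of operator freedom is unknown.
- **A reader might also infer that displacing one voxel would reproduce the pilot's pSN change.** The documents do not support this. They give no FW contrast between neighbouring voxels, moving a fixed block exchanges several voxels at once, and the pilot figure is a mean of two patients.
- **Not every MRI outcome is exposed to the reader.** Correct: mainly the pSN, the DMN-T through edits, and the nbM little.
- **The filter comparison is conditional.** It assumes that an occipital artefact carries over proportionally to regions with other baselines. The bias also needs a shift in one direction across patients, whereas the pilot values ran both ways. Both limits stand.
- **The sign of the rule is clear enough.** Largely accepted. The pilot range is given with signs just before the rule, so counting both falls and rises is the natural reading.

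**Conclusion.** The point holds in a limited form. No masking to visit order is planned where it is the only masking possible, and this exposes the pSN and, less so, the DMN-T. The size of any reader effect cannot be derived from the documents.

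The 14% cut-off is 1.21 times the one-year pSN change and 2.6 times the pro-rata 24-week change. If a fall just under it were shared by all 15 patients and lithium did nothing, the chance of a significant apparent benefit against PPMI would be 29% to 55% instead of 2.5%; with a shared 8% fall, 13% to 22%. These figures rest on linear change, a proportional artefact, an inferred baseline of 0.155 and, for the upper values, an assumed 24-week SD. They describe what the rule would allow, not what is expected.

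A reader might conclude that the MRI results are bound to be biased, or that artefacts within the filter could in general produce the whole effect. The documents do not support that: shifts that differ at random between patients leave the mean unbiased and barely widen the SD, and nothing shows that a shared shift occurred in the pilot.

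**What to change.** 1. **Mask the reading.** Give the imaging centre each scan under a random code, with date and visit removed and the order shuffled. Lock region placement, manual edits and quality exclusions before the visit key is released. This takes header stripping and a key holder; no extra reader or scan is needed.
2. **Clarify and supplement the occipital rule.** State that the 14% applies to the absolute change. Pre-specify sensitivity analyses on the trial's own data: either region change minus occipital change (stating the scale), or the treated-group mean region change estimated at zero occipital change. Report results with and without excluded patients.

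**Cost.** The regression uses one degree of freedom, and its estimate at zero is imprecise if nearly all patients share the same shift. Subtraction covers that case but adds occipital measurement noise and would also remove any genuine brain-wide change. Both therefore belong in sensitivity analyses, not in place of the main one. Adjusting the external comparators as well is possible only if their patient-level occipital data can be obtained; the plan gives only one aggregate PPMI figure and none for UF.
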